6.4. PK Endpoints

- Plasma concentrations of PF-06651600 at Weeks 4, and 8 or 12.
- Population: PK analysis set.
- Statistical Method: Descriptive statistics of plasma concentrations of PF-06651600 at Weeks 4, and 8 or 12. Population PK model detailed in a separate PK analysis plan.

6.5. Subset Analyses

Summary statistics for SALT ≤ 20 at week 24, SALT ≤ 10 at week 24 and PGI-C response at Week 24 will be presented by subgroups as below:

- Age (years) at baseline (12-17, ≥ 18);
- Age (years) at baseline (12-17, 18-44, 45-64, ≥ 65);
- Body Mass Index (BMI) group at baseline (< 25 , 25-30, ≥ 30);
- Weight at baseline ($<$ median, \geq median);
- Gender (Male, Female);
- Race (White, Black, Asian, Other);
- Region of enrollment (North America, Europe, Asia, Rest of World) as specified in [Section 9.4](#);
- Baseline disease severity (AT/AU, non AT/AU);
- AA duration since first diagnosis (years) ($<$ median, \geq median);
 - The median of the entire sample will be used as the cut-off value.
- Duration of onset of current AA episode (years) ($<$ median, \geq median);
 - The median of the entire sample will be used as the cut-off value.
- Prior pharmacological treatment of AA (yes, no); [Section 9.7](#).

Estimates of the response rates for each dose compared to the placebo group and its 95% CI based on MN method, will be presented for each defined category of each subgroup. No p-values will be presented.

The primary purpose of the subgroup analyses is to check for consistency of results across subgroups. There is no intention to have any specific inference within subgroups. The analysis described in this SAP may be repeated on the specific country and/or region subpopulation sets in order to meet country-specific regulatory requirements.

6.6. Baseline and Other Summaries and Analyses

6.6.1. Baseline Summaries

Medical history will be summarized by treatment group using frequency and percentage of subjects for each medical condition according to Pfizer Standards. Demographics will be summarized by treatment group. Continuous demographics characteristics data, such as age will be summarized using descriptive statistics. Categorical data such as gender will be summarized using frequency and percentages.

Targeted medical history using the list in [Section 9.5](#) will also be summarized.

6.6.2. Study Conduct and Subject Disposition

Subjects evaluation, disposition, discontinuation will be summarized according to Pfizer standards.

6.6.3. Study Treatment Exposure

A summary of compliance and the number of doses received as well as the median total dose by treatment group will be provided.

The exposure to study drug will be summarized by the total number of days of dosing.

6.6.4. Concomitant Medications and Non-Drug Treatments

Prior drug and non-drug treatment, concomitant drug and non-drug treatment will be summarized according to Pfizer standards.

6.7. Safety Summaries and Analyses

Safety analysis will be based on the safety analysis set (SAS).

Safety data will be presented in tabular and/or graphical format and summarized descriptively, where appropriate. All safety endpoints will be listed and summarized in accordance with Pfizer Standards. Categorical outcomes (eg, AEs) will be summarized by subject counts and percentage. Continuous outcome will be summarized using N, mean, median, standard deviation, etc. Selected subject listings will be produced for these safety endpoints accordingly.

In order to report the impact of COVID-19 on clinical trial populations and study data, the following additional listings and summaries will be produced:

- Listing of subjects affected by COVID-19 related study disruption;
- Protocol deviations related to COVID-19;
- Summary of drug interruption before and after the COVID-19 pandemic anchor date (09 January 2020 for Taiwan/China sites, and 11 March 2020 for the remaining countries);

- Discontinuations from study drug due to COVID-19 related AEs.

6.7.1. Adverse Events

The safety data will be summarized in accordance with Pfizer Standards. Adverse events of special interest will be summarized based on a list of preferred terms that will be provided by safety risk lead to the programming team prior to database lock. All safety data will be summarized descriptively through appropriate data tabulations, descriptive statistics, categorical summaries, and graphical presentations. Safety endpoints for the study include:

- Treatment-emergent (including treatment-related) AEs and SAEs;
- AEs leading to discontinuation;
- AEs will be displayed for the following periods: Baseline to Week 24, and Baseline to Week 48;
- Treatment-emergent COVID-19 related AEs by SOC and PT;
- Summary of TEAE before and after the COVID-19 pandemic anchor date.

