## 1.5. Study Rationale

This study is being conducted to evaluate the efficacy and safety of multiple doses/regimens of PF-06651600 in comparison with placebo over the first 24 weeks treatment duration. This will be followed by an additional 24-week extension period during which all subjects will receive active treatment including those subjects who received placebo during the initial 24 weeks of the study.

This study will test multiple dose regimens, including the dose regimen with demonstrated clinical efficacy in the ongoing Phase 2a Study B7931005, as well as several lower doses to evaluate dose-response relationships. The rationale for selection of the dosing regimens in this study is further described in [Section 1.6](#).

In addition to dose-ranging, the other objectives of this study are to support registration for treatment of patients with moderate to severe AA and to evaluate safety in this population. To achieve this, response based on absolute SALT score  $\leq 20$  at Week 24 will be the primary endpoint for analyzing a dose-response and for confirming a clinically meaningful treatment effect in patients with AA. SALT is an instrument that is widely used to assess severity of AA by visual determination of the amount of terminal hair loss and summing across four views of the scalp (left side, right side, top and back; range 0-100%). This tool has been well accepted and used in multiple AA clinical trials (NCT02691117; NCT01950780; and NCT01797432) as a reliable and reproducible measure of disease severity.

The extension phase of this study will provide additional blinded safety and efficacy data, including long-term data in subjects initially randomized to active treatment as well as data in subjects initially randomized to placebo and subsequently advanced to active treatment at Week 24.

The total sample size for the study is approximately 660 randomized subjects.

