**Table 2. Number and Type of Tablets for Each Treatment Sequence**

Treatment Sequence	Loading Period Day 1 to Week 4 (No. of Tablets)	Maintenance Period Weeks 4 to 24 (No. of Tablets)	First 4 Weeks of Extension Period Weeks 24 to 28 (No. of Tablets)	Remainder of Extension Period Weeks 28 to 48 (No. of Tablets)
A	4 of 50 mg active 3 of 10 mg size pbo	1 of 50 mg active 3 of 10 mg size pbo	1 of 50 mg active 3 of 50 mg size pbo 3 of 10 mg size pbo	1 of 50 mg active 3 of 10 mg size pbo
B	4 of 50 mg active 3 of 10 mg size pbo	1 of 50 mg size pbo 3 of 10 mg active	4 of 50 mg size pbo 3 of 10 mg active	1 of 50 mg size pbo 3 of 10 mg active
C	1 of 50 mg active 3 of 50 mg size pbo 3 of 10 mg size pbo	1 of 50 mg active 3 of 10 mg size pbo	1 of 50 mg active 3 of 50 mg size pbo 3 of 10 mg size pbo	1 of 50 mg active 3 of 10 mg size pbo
D	4 of 50 mg size pbo 3 of 10 mg active	1 of 50 mg size pbo 3 of 10 mg active	4 of 50 mg size pbo 3 of 10 mg active	1 of 50 mg size pbo 3 of 10 mg active
E	4 of 50 mg size pbo 1 of 10 mg active 2 of 10 mg size pbo	1 of 50 mg size pbo 1 of 10 mg active 2 of 10 mg size pbo	4 of 50 mg size pbo 1 of 10 mg active 2 of 10 mg size pbo	1 of 50 mg size pbo 1 of 10 mg active 2 of 10 mg size pbo
F	4 of 50 mg size pbo 3 of 10 mg size pbo	1 of 50 mg size pbo 3 of 10 mg size pbo	4 of 50 mg active 3 of 10 mg size pbo	1 of 50 mg active 3 of 10 mg size pbo

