2.2. Study Design

This is a Phase 2b/3, randomized, double-blind, placebo-controlled, dose-ranging study to investigate PF-06651600 in subjects with AA. The study will have a maximum duration of approximately 57 weeks. This includes an up to 5-week Screening period, a 48-week treatment period, and a 4-week follow-up period as shown below. The treatment period will be comprised of a placebo-controlled period that includes a 4-week loading phase and a 20-week maintenance phase, followed by a 24-week extension phase. The study will enroll a total of approximately 660 subjects. The study will be conducted at approximately 120 sites.

Figure 1. Study Design Schematic

* Primary endpoint is response based on absolute Severity of Alopecia Tool (SALT) Score ≤ 20 at Week 24.

To be eligible to enroll in this study, subjects must have moderate to severe AA with $\geq 50\%$ hair loss of the scalp (Severity of Alopecia Tool [SALT] score ≥ 50) at both Screening and baseline visits, without evidence of terminal hair regrowth within the previous 6 months, and with the current episode of hair loss ≤ 10 years.

Screening will occur within 35 days prior to the first dose of study drug to confirm that subjects meet selection criteria for the study. Eligible subjects will be randomized as described below.

A stratified randomization will be used for operational purposes in order to achieve a target global composition for AT/AU and adolescent subjects in the enrolled population. The targets for enrollment are approximately 40% AT/AU and approximately 15% adolescents. The randomization will be operationalized as follows. In regions enrolling both adolescents and adults, there will be four strata:

- <18 years of age and AT/AU;
- <18 years of age and not AT/AU;

- ≥ 18 years of age and AT/AU; and
- ≥ 18 years of age and not AT/AU.

Within each of these strata, subjects will be randomized in a 2:2:2:2:1:1:1 manner to blinded PF-06651600 and matching placebo for a total of 7 treatment sequences. In regions enrolling only adults, there will be two strata:

- ≥ 18 years of age and AT/AU; and
- ≥ 18 years of age and not AT/AU.

In these regions, subjects will be randomized using the same ratio as described for regions enrolling both adolescents and adults.

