All subjects will begin dosing during the loading phase according to their assigned sequence. Following the 4-week loading phase, subjects will continue dosing according to their assigned sequence in the 20-week maintenance phase. At the end of the maintenance phase, placebo-treated subjects will be advanced in a prespecified, blinded manner to one of 2 active treatment sequences for the remainder of the study (through Week 48). Investigators, subjects, and the sponsor study team will be blinded to treatment throughout the duration of the study. Following the last dose of study drug, both discontinued and completed subjects will enter a 4-week follow-up period for safety monitoring. Subjects who complete treatment may be eligible for enrollment in a long-term study (Phase 3 study B7981032). Subjects who enroll immediately into B7981032 study will not be required to complete the 4-week follow-up period in this study.

The study may be unblinded for internal decision-making purposes when $\geq 90\%$ of subjects have reached 24 weeks post-randomization (or discontinued prior to the Week 24 visit). The sponsor personnel who are unblinded will be separate from the study team. The sponsor will still maintain the blind for study team members who will be involved in daily study conduct, study management, safety, and data monitoring through the completion of the study. Investigators and subjects will remain blinded.

Early unblinding for PK/PD modeling purposes is planned when $\geq 90\%$ of subjects have reached 24 weeks post-randomization (or discontinued prior to the Week 24 visit). There will be no impact on B7981015 study conduct, analysis, or reporting based on the early unblinding of the PK/PD data. The results of these analyses will be reported in a separate pharmacometrics analysis report.

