3.4.1. Adverse Events

An AE is considered a treatment emergent adverse event (TEAE) if the event starts on or after the first dosing day.

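### The SAP specifies no adverse event table that isolates time on drug after the placebo sequences switch at Week 24

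*SAP*

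**What the plan says.** SAP 6.7.1 gives the reporting periods: "AEs will be displayed for the following periods: Baseline to Week 24, and Baseline to Week 48". Both start at baseline. SAP 3.4.1 defines treatment emergence by a single anchor: "An AE is considered a treatment emergent adverse event (TEAE) if the event starts on or after the first dosing day". SAP 6.7 reports adverse events as subject counts and percentages in the safety analysis set. SAP 4.3 defines that set as everyone with at least one dose of study medication, placebo included.

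On the switch, SAP 2.2 says: "At the end of the maintenance phase, placebo-treated subjects will be advanced in a prespecified, blinded manner to one of 2 active treatment sequences". Protocol Table 2 shows only placebo tablets for F and G up to Week 24. For Weeks 24 to 28 sequence F then takes "4 of 50 mg active 3 of 10 mg size pbo", while G takes a single 50 mg active tablet with placebo.

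SAP 5.2 pools F and G for comparisons with placebo up to Week 24 and shows seven separate sequences for analyses up to Week 48. Protocol 1.5 lists, among the safety and efficacy data the extension is to provide, "data in subjects initially randomized to placebo and subsequently advanced to active treatment at Week 24".

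**The concern.** For A to E, the 48-week display is a sensible long-term summary of a single assigned active regimen. For F and G it is not: half of the planned observation time is placebo time, and nothing in SAP 6.7 or Protocol 9.5 separates the halves. The TEAE anchor is not reset at the first extension dose. The only other split of adverse events in SAP 6.7.1 is before and after a COVID-19 anchor date, which is a calendar date unrelated to the switch.

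The denominator has a related fault. A subject in F or G who stops before Week 24 never takes active drug but still counts in the 48-week row.

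At stake is the adverse event incidence on drug in the subjects who first receive it at Week 24, which is one of the things the extension is meant to show. The SAP does handle the change elsewhere. SAP 5.2.3 restricts the 48-week repeated-measures model to the initial active groups, Section 6 treats Weeks 25 to 48 as a separate period for point estimates, and SAP 9.1 derives the day of the first extension dose (EDay 1). The adverse event rule uses none of this.

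**Working it through.** **1. Number of subjects.** SAP 2.2: "The study will enroll a total of approximately 660 subjects", and "subjects will be randomized in a 2:2:2:2:1:1:1 manner". The ratio sums to 2+2+2+2+1+1+1 = 11, and 660/11 = 60. So A to D have 120 each and E, F and G have 60 each, which returns the total: 4 × 120 + 3 × 60 = 660. F and G together have 120 randomized subjects.

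**2. Share of placebo time.** The treatment period is a 4-week loading phase, then a "20-week maintenance phase, followed by a 24-week extension phase". Placebo time in F and G is 4 + 20 = 24 weeks out of 48, or 50% for a subject with full follow-up.

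**3. What the 48-week row estimates.** Let p0 be the probability of at least one event in the 24 placebo weeks and p1 the probability in the 24 active weeks. Assuming independence and full follow-up, the 48-week percentage is 1 − (1 − p0)(1 − p1). The quantity wanted is p1.

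**4. Whether subtraction recovers p1.** The 48-week percentage minus the 24-week percentage is (1 − p0)p1. It counts only subjects whose first event came after the switch, so it misses a share p0 of the post-switch cases. The first three rows below use assumed incidences that are not in the documents. The last uses the any-TEAE figures in Protocol 1.4.1.

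| p0 | p1 | 48-week row | Subtraction | Share missed |
|---|---|---|---|---|
| 5% | 10% | 14.5% | 9.5% | 5% |
| 10% | 20% | 28.0% | 18.0% | 10% |
| 20% | 40% | 52.0% | 32.0% | 20% |
| 74.5% | 62.5% | 90.4% | 15.9% | 74.5% |

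For the last row: 1 − 0.255 × 0.375 = 0.904, and 0.904 − 0.745 = 0.159. In a sequence of 60 that is about 60 × 0.159 = 9.6 subjects, against 60 × 0.625 = 37.5.

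**5. Dependence on independence.** Events in the two halves are probably correlated within a subject. For the any-TEAE row this does not rescue subtraction. Only 1 − 0.745 = 25.5% of subjects could still become new cases, so the difference lies between 0 and 25.5% under any correlation and cannot reach 62.5%.

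**6. Dropout.** If a fraction d leaves F or G before the first extension dose, the 48-week denominator still includes them. Even a clean count of post-switch cases would then be diluted by the factor 1 − d. The documents give no value for d.

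**The case against.** The strongest reply is that the SAP's list is not exhaustive. SAP 6.7 also promises listings and summaries under sponsor standards that are not in the documents, so a post-switch output may exist. That stands against any claim that none will be produced. It does not supply a specified table, and 6.7.1 names its periods explicitly. Rebuilding incidence from dated listings is not a planned analysis.

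Second, a reader might infer that safety after the switch cannot be seen at all. The documents do not support this. SAP 6.7.3 summarizes vital signs at all post-baseline visits, and the windows in SAP 9.1 place data from Week 26 onward after EDay 1 for any safety data shown by visit.

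Third, subtraction often works. The pooled F and G count at Week 24 can be taken from the sum of F and G at Week 48, and for uncommon events the loss is small (5% of cases at p0 = 5%). For events leading to discontinuation it is nearly exact, because a subject withdrawn before Week 24 does not enter the extension. This stands. It leaves common events unresolved, and also the split between F and G if the Week 24 pooling rule is applied to safety.

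Fourth, the 200 mg start is already observed against concurrent placebo in A and B, about 240 subjects, in the first 24-week display. So sequence F is not the only source on it.

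Fifth, Protocol 1.5 also names long-term data in subjects first assigned to active drug. For them the 48-week display is appropriate.

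**Conclusion.** The gap is real and limited to adverse event incidence tables. As specified, the 48-week percentages for F and G mix equal planned periods of placebo and drug, over a denominator that includes subjects never given drug. No specified table gives incidence after the switch. The number affected is at most about 120, since this is the randomized count before dropout.

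The size of the distortion depends on how common the event is. It is minor for rare events if the reader subtracts the displays, and severe for the any-TEAE row (about 16% against 62.5%). That illustration borrows rates from a separate Phase 2a study with 47 placebo and 48 active subjects and assumes independence and full follow-up. It would be tempting to conclude that active treatment could add at most a quarter of subjects in every row. That ceiling belongs to the any-TEAE row alone and does not carry over to serious or uncommon events.

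No efficacy inference is affected. The change is worth making because it serves a stated purpose of the extension at almost no cost.

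**What to change.** Add to SAP 6.7.1 an adverse event display from the first extension dose (EDay 1, as derived in SAP 9.1) to Week 48, by treatment sequence, with subjects dosed in the extension as the denominator. For F and G, count only events that start on or after EDay 1, which matches the on-or-after convention in SAP 3.4.1. Keep the two existing displays: the first gives the placebo-controlled comparison, and the second suits the sequences on active drug throughout. Add a footnote to the F and G columns of the 48-week display saying that they include placebo time. Exposure-adjusted rates for the 48-week period are optional, since the new display removes the mixing without them.

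The cost is one extra set of adverse event tables and a short SAP edit. Onset dates and EDay are already available, so no new data are needed.

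### Before/after COVID-19 summaries of adverse events and drug interruptions carry no time at risk, so the two percentages can differ substantially with no change in event rate

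*SAP*

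**What the plan says.** SAP 6.7 introduces a group of COVID-19 outputs "In order to report the impact of COVID-19 on clinical trial populations and study data". One is a "Summary of drug interruption before and after the COVID-19 pandemic anchor date". The date is 9 January 2020 for sites in Taiwan and China and 11 March 2020 elsewhere. SAP 6.7.1 adds a "Summary of TEAE before and after the COVID-19 pandemic anchor date".

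On format, SAP 6.7 states: "Categorical outcomes (eg, AEs) will be summarized by subject counts and percentage". It also says: "Safety data will be presented in tabular and/or graphical format and summarized descriptively, where appropriate". No test or estimated before/after difference is planned.

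On exposure, SAP 6.6.3 says: "The exposure to study drug will be summarized by the total number of days of dosing". That total is not split at the anchor date. The treatment-emergent definition in SAP 3.4.1 looks only at whether onset is on or after the first dosing day. No section gives a denominator for each period, person-time, or a rule for subjects whose follow-up spans the date.

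**The concern.** The other adverse event displays use study-time windows that are the same for everyone, so a percentage of subjects is a natural measure there. A calendar split is different. A subject who enrolled early may have nearly all follow-up before the date, and one who enrolled late may have nearly all of it after. The chance of at least one event in a period grows with the length of that period, so the two percentages can differ when the underlying rate is the same.

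Uneven follow-up is plausible here. The protocol's Document History mentions a letter to active sites dated 16 November 2018, 481 days (about 69 weeks) before 11 March 2020. A subject has at most 48 + 4 = 52 weeks after first dose (SAP 2.2), so someone enrolled at that time could have no follow-up after the date. Protocol Appendix 6.1 sets conditions for enrolling during the pandemic, so subjects with no time before the date were also foreseen.

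Treatment changes over the same time. Subjects randomised to placebo move to active drug after Week 24. For those whose follow-up spans the date, before versus after is partly placebo versus active.

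At stake is whether these tables can serve their stated purpose. A reader could take a follow-up artefact for a pandemic effect, or miss a real one.

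**Working it through.** The plan states no figure for these summaries, so there is none to reproduce. The check asks what the planned format would show if the pandemic changed nothing.

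**Inputs**
- Anchor date: 11 March 2020 (SAP 6.7).
- Follow-up: up to 52 weeks after first dose (SAP 2.2).
- Event frequency: 62.5% of actively treated subjects with a treatment-emergent event in 24 weeks, from the Phase 2a study (protocol 1.4.1). Used for illustration only.
- Enrolment: not in the documents. Assumed uniform, starting November 2018, January 2019 or March 2019 and ending December 2019, 11 March 2020, June 2020 or October 2020.

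**Formula**
- Constant weekly rate: λ = -ln(1 - 0.625)/24 = 0.0409.
- Chance of at least one event in a period of T weeks: 1 - exp(-λT).

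**One subject, 52 weeks, no change in rate**

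| Share of follow-up before / after | Before | After |
|---|---|---|
| 20 / 80 | 34.6% | 81.7% |
| 35 / 65 | 52.5% | 74.9% |
| 50 / 50 | 65.4% | 65.4% |
| 65 / 35 | 74.9% | 52.5% |
| 80 / 20 | 81.7% | 34.6% |

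For the first row, 20% of 52 weeks is 10.4 weeks, and 1 - exp(-0.0409 × 10.4) = 34.6%.

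**Averaged over assumed enrolment windows, no change in rate**

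| Denominator | Enrolment window | Before | After | Difference (points) |
|---|---|---|---|---|
| All treated | Nov 2018 to Dec 2019 | 74.5% | 35.9% | -38.6 |
| All treated | Mar 2019 to Oct 2020 | 36.7% | 68.7% | +32.0 |
| At risk in the period | Nov 2018 to Dec 2019 | 74.5% | 52.1% | -22.4 |
| At risk in the period | Nov 2018 to Jun 2020 | 66.4% | 65.5% | -0.9 |
| At risk in the period | Mar 2019 to Oct 2020 | 59.5% | 70.1% | +10.6 |

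An at-risk denominator reduces the artefact but does not remove it. Depending on the window, 50% to 97% of subjects have follow-up on both sides of the date.

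**Against a real effect.** A true 25% rise in rate after the date moves the at-risk after percentage by only about 6 to 7 points. In the November 2018 to December 2019 window it would read 74.5% before and 58.7% after, which is the wrong direction.

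**Drug interruptions.** Assume 10% of subjects interrupt per 52 weeks, so λ = -ln(0.9)/52 = 0.0020 per week, with enrolment from January to December 2019. The at-risk percentages are 6.8% before and 4.1% after with no true change.

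**With person-time.** The same adverse event inputs give 0.0409 × 52.18 × 100 ≈ 213 events per 100 patient-years on both sides in every window, a ratio of 1.0.

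**The case against.** The strongest reply has five parts.

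- **No comparison is planned.** The tables are descriptive. This stands, and it limits the consequence. But the stated purpose is to report the impact of COVID-19, and a before/after table invites that reading.
- **The denominator is not stated.** The SAP also says: "All safety endpoints will be listed and summarized in accordance with Pfizer Standards". Those standards are not in the documents and might define period denominators. So a reader who assumes one fixed denominator for both periods goes beyond the text. The percentage format is explicit for adverse events and only inferred, from the general rule on categorical outcomes, for drug interruptions. What remains is that at-risk denominators alone still leave up to about 22 points of artefact.
- **The size depends on unknown enrolment dates.** A reader might infer that the tables mainly measure follow-up. The documents do not support that, because with balanced follow-up the artefact almost vanishes.
- **Arms should be affected alike.** A reader might infer a bias between arms. Randomisation is concurrent and stratified, so calendar follow-up should be similar across groups. A difference would come mainly from differential dropout, and nothing in the documents shows it.
- **COVID-19 is also reported directly.** The SAP plans a listing of affected subjects, COVID-19 protocol deviations, discontinuations for COVID-19 related events, and COVID-19 related events by system organ class and preferred term. None of these depends on the split.

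It is also tempting to say that time before the date holds the early and loading phases. That is not general. Subjects enrolled after the date have all their early time after it, and protocol Table 2 shows sequence F taking four 50 mg active tablets daily in Weeks 24 to 28.

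**Conclusion.** The point holds as a minor one about two supplementary safety summaries. Under the stated format, the percentages before and after the anchor date can differ by tens of points, in either direction, with an unchanged event rate. They can also nearly agree. Without time at risk in each period, a reader cannot tell which case applies, so the display cannot reliably show the impact of COVID-19.

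The sizes rest on a constant event rate borrowed from the Phase 2a study, full 52-week follow-up, and uniform enrolment over assumed windows. They show a range and do not predict this trial's tables.

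A reader might infer that the safety conclusions are compromised. They are not. The adverse event tables for Baseline to Week 24 and Baseline to Week 48 use fixed study-time periods, and no efficacy analysis or hypothesis test uses the calendar split.

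**What to change.** Amend SAP 6.7 and 6.7.1 so that, for the before/after summaries:

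1. each event is assigned to a period by its onset date;
2. only subjects with at least one day at risk in a period are counted in it;
3. patient-years are shown for each period;
4. exposure-adjusted incidence is reported, as events or first events within the period per 100 patient-years at risk, by treatment group;
5. results are given separately for the placebo-controlled and extension phases where numbers allow, because person-time removes the follow-up artefact but not differences in phase or treatment received;
6. drug interruptions are handled in the same way.

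If the sponsor's reporting standards already define these denominators, the SAP should say so.

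The cost is SAP wording and slightly more programming, using dosing and event dates already collected. The downside is some sparse cells: under the 2:2:2:2:1:1:1 allocation of about 660 subjects, the three smaller sequences have about 660/11 = 60 subjects each.
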